3.4 Sponsor Responsibilities

General Responsibilities:

As the Sponsor, ZELTIQ Aesthetics assumes overall responsibility for the conduct of the study. ZELTIQ Aesthetics assumes all responsibilities per 21 CFR 812 and other applicable regulations, and shall:

IRB approval: Ensure IRB approval for the investigation before shipping the device to any Investigator.

Investigators: Select Investigators qualified by training and experience, and providing them with the information they need to conduct the investigation properly (21 CFR 812.43). Obtain a signed Investigator Agreement (21 CFR 812.43(c)) from each participating Investigator. Study sites will be evaluated to ensure that they have an adequate patient base and can provide sufficient staff and documentation support to conduct the study properly.

Monitoring: Select monitors qualified by training and experience to monitoring the study (21 CFR 812.43), and ensure proper monitoring of the investigation (21 CFR 812.46).

Investigational devices: Provide devices only to qualified Investigators (21 CFR 812.43). No study site may receive shipment of study devices until the following documents are received by the Sponsor:

- Signed Investigator's Letter of Agreement
- Signed Clinical Site Agreement
- Investigator current curriculum vitae

Data Management and analysis: Ensure data collection, verification, analysis, records storage, etc. Sponsor will assist with presentation(s) and/or publication(s).

Training

Study Training: To ensure uniform data collection and protocol compliance, Sponsor personnel will provide an educational session to study site personnel as needed, which will cover the Investigational Plan, techniques for the identification of eligible subjects, data collection and form completion, and the device directions for use. The Investigator and study staff will be trained on the study devices and protocol, applicable regulations and requirements, and expectations of the study, enrollment expectations, subject selection, informed consent, required clinical data and record keeping, etc.

Investigational Device Use: Representatives of the Sponsor will train Investigators in use of the study device prior to study initiation. Sponsor representatives may be present at study procedures.

Site Monitoring

The Sponsor will ensure that qualified clinical monitors are available to monitor and oversee the conduct of the trial and that monitoring is performed in accordance with the Sponsor's approved procedures or third-party procedures approved by the Sponsor.

The clinical monitors will evaluate compliance with the investigational plan, FDA regulations, any specific recommendations made by the site's IRB and the signed Investigator Agreement.

Monitoring Visits

On-site monitoring visits will assess the progress of the clinical study and identify any concerns that result from device performance or review of the Investigator's study records, study management documents, and informed consent documents.

Monitoring will ensure continued protocol compliance, accurate data reporting, and adequate accounting of shipments of study devices. Monitoring visits will occur at minimum once before study close-out.

During monitoring visits, the monitor will compare subject records and other supporting documents with reports at the site to determine that;

- The facilities used by the investigation continue to be acceptable for the purposes of the clinical study

ZELTIQ P/N: [REDACTED]
Protocol Number: ZA19-002

- Informed consent was properly obtained and documented for all enrolled study participants
- The Investigational Plan is being followed, and only eligible subjects are being enrolled into the study
- Deviations to the Investigational Plan have been reported to ZELTIQ and the IRB, as appropriate
- Adverse events are promptly being reported
- Device accountability is being maintained
- Information recorded in the case report forms and study reports are accurate, complete, legible and consistent with source documentation.
- Subjects failing to complete the clinical study and the reason for failure are recorded.
- Missed follow-up visits are noted in the study documentation

Clinical monitors will provide feedback to the site regarding protocol or study compliance.

Study Site Closeout

At the close of the study at an investigational site, the monitor will ensure that all case report forms have been monitored and retrieved and that the Investigator's files are accurate and complete. The monitor will ensure that all investigational devices and study supplies are accounted for and provide for appropriate disposition of any remaining supplies. The monitor will review record retention requirements with the Investigator and any remaining Investigator obligations are reviewed and ensure that all applicable requirements are met for the study. The monitor will prepare a report of the site closeout visit.

Final Report

A final report will be prepared at the conclusion of the trial. Copies of the final report will be provided to each Investigator and to the respective IRB.

4. Data Ownership

ZELTIQ Aesthetics, the study Sponsor, retains ownership of all data generated in this study, and controls the use of the data for purposes of regulatory submissions to the US and/or other governments. Investigator(s) and institution(s) (which shall include their employees, agents, and

representatives) may not issue or disseminate any press release or statement, nor initiate any communication of information regarding this study (written or oral) to the communications media or third parties without the prior written consent of the Sponsor.

5. Publication Policy

Participating Investigators and/or Institutions may publish information or data collected or produced as a result of participation in appropriate scientific conference or journals or other professional publications subject to written permission from the Sponsor, provided that drafts of the material are provided to the Sponsor for purposes of review and comment at least sixty (60) days prior to the first submission for publication or public release. Investigators may not publish information regarding site-specific data until a multicenter study report has been published.

6. Risk/Benefit Analysis

The Sponsor has undertaken a comprehensive risk-benefit analysis.

6.1 Benefits

Muscle toning and contouring in the treatment area is anticipated to provide an aesthetic benefit and the EMS device is a non-invasive device that accomplishes the desired effect without anesthesia and with minimal-to-no recovery time. [REDACTED]

[REDACTED]
[REDACTED]
[REDACTED] Considering the number of body contouring surgical procedures performed for the removal of fat each year (1.3 million procedures worldwide, according to the 2011 International Society of Aesthetic Plastic Surgeons Biennial Global Survey), the use of such a non-invasive procedure has the potential to significantly reduce the incidence of complications and post-surgical limitations associated with those procedures.

6.2 Risks

Although this study presents minimal risks to the subject, there is always the potential for some risk when a medical procedure is performed. Per manufacturers' user manuals, side effects of EMS treatment includes muscular pain, temporary muscle spasm, temporary joint or tendon pain, and local erythema. Scientific literature regarding use of EMS devices for aesthetic purposes to tone and strengthen abdominal and gluteal muscle describe mild muscle soreness, minor discomfort during treatment^[4-8].

Anticipated Device Effects of EMS:

ZELTIQ P/N: [REDACTED]
Protocol Number: ZA19-002

- muscular pain in the treatment area
- temporary muscle spasm
- temporary joint or tendon pain
- local erythema and/or skin redness
- muscular contraction adjacent to the treatment area during treatment

Adverse Effects

The following summarizes the potential adverse effects in this study:

Potential Adverse Effect	Description
Severe Erythema	The appearance of erythema (redness) that is rated as severe by the Investigator
Prolonged Erythema	Erythema lasting longer than 2 weeks.
Infection	Infection at the treatment site, diagnosed by a physician and requiring medical intervention.
Discomfort During Procedure	Discomfort during the procedure that is intolerable to the subject and results in discontinuation of the procedure.
Discomfort Post Procedure	Significant discomfort, pain, cramping, tenderness, soreness, muscle spasm following the procedure which results in medical intervention (physician visit and/or prescription pain reliever)
Sensory Alteration Outside Treatment Area	Sensory or motor nerve alteration that does not resolve within twenty minutes following applicator removal.
Nerve injury	Injury to the motor nerves that innervate the legs.
Vasovagal Symptoms	The occurrence of symptoms of anxiety, lightheadedness, dizziness, nausea, sweating, near syncope, or syncope (fainting).
Gynecological symptoms	Menstrual cycle irregularity
Allergic/Irritant Contact Dermatitis	Itchy rashes and skin peeling that may result exposure to wrap/bonnet material or applicator pressure
Hernia	Exacerbation of hernia. Hernia is defined as a protrusion of an organ or the fascia of an organ through the wall of the cavity that normally contains it.
Other	Any other untoward medical event determined by the Investigator to be an adverse event, regardless of the relationship to the device or treatment.

7. Selected References

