- b) Repeat pregnancy test for female subjects of childbearing potential (urine). Exclude subject from participation if the results are positive.

EMS Treatment Steps

- c) Apply EMS device per manufacturer's Instructions for Use.
- d) Support the EMS device with pillows or straps as needed.
- e) Initiate treatment using recommended program for toning and firming the targeted treatment area supplied by manufacturer.
- f) Record the highest percent (%) energy utilized for the EMS treatment.
- g) [REDACTED]
[REDACTED]
[REDACTED]

Post-EMS Treatment # 4

- h) Subject completes Body Satisfaction Scale(s) (for abdomen and/or buttocks, as appropriate)
- i) [REDACTED]
[REDACTED]
- j) Optional - Obtain 2-Dimensional photographs of the treatment area using standardized setup and settings.

The need for post-treatment care is not expected following the EMS treatments performed in this study. Subjects will be encouraged to call the study site if they experience any unusual effects (e.g., severe discomfort etc.), which may be related to the study.

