2.18 Adverse Events

Adverse events (AEs) will be assessed continuously throughout the study. An adverse event is defined as any untoward medical occurrence in a participant, regardless of whether the event is related to the device.

All AEs and device deficiencies will be recorded on the corresponding CRF for the subject.

Adverse Device Effect (AE)

Any sign, symptom, or disease in a study participant that occurs during the course of a clinical trial that is determined by the Investigator to have a causal relationship or possible causal relationship with the device under investigation.

Device Deficiencies

A device deficiency is defined in accordance with ISO 14155 as inadequacy of a medical device including issues with respect to its identity, quality, durability, reliability, safety, or performance. Device deficiencies include malfunctions, use errors, and inadequate labeling.

If a device deficiency occurs, the investigational site will document the event using the CRF. Device deficiencies will be documented throughout the study and appropriately managed and reported to regulatory authorities and IRBs as required by Federal regulations.

Serious Adverse Event (SAE)

Any untoward medical occurrence in a participant, regardless of whether the event is related to the device that:

- a. results in death;
- b. results in a life-threatening illness or injury;

The term life threatening in the definition of serious refers to an event in which the participant was at risk of death at the time of the event. It does not refer to an event, which hypothetically might have caused death, if it were more severe.

- c. results in a permanent impairment of a body structure or body function;
 - Impairment of body function means a substantial disruption of a person's ability to conduct normal life functions.
 - This definition is not intended to include experiences of relatively minor medical significance such as uncomplicated headache, nausea, vomiting, diarrhea, influenza, and accidental trauma (e.g., sprained ankle) which may interfere with or prevent everyday life functions but do not constitute a substantial impairment.
- d. requires in-patient hospitalization or prolongation of existing hospitalization;
 - In general, hospitalization signifies that the participant has been detained (usually involving at least an overnight stay) at the hospital or emergency ward for observation and/or treatment that would not have been appropriate in the physician's

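### Do the thresholds in the Section 6.2 risk summary keep mild, expected device effects out of the primary safety endpoint?

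*Combined protocol and SAP*

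**What the plan says.** Sections 2.15.1 and 2.16.3 make the frequency of device-related AEs, serious ones included, the primary safety endpoint. It is summarized descriptively, as the number and percentage of subjects with each type of event.

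Section 2.18 supplies the definitions and the recording rule:

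- The definition: "An adverse event is defined as any untoward medical occurrence in a participant, regardless of whether the event is related to the device".
- The recording rule: "All AEs and device deficiencies will be recorded on the corresponding CRF for the subject".
- An adverse device effect is any clinical manifestation that the Investigator judges causally, or possibly causally, related to the device. No severity or duration condition is attached.
- Non-serious events must reach the Sponsor within one week of the site learning of them.

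Section 6.2, in the risk/benefit chapter, has two lists. The first holds five anticipated device effects, among them "muscular pain in the treatment area", temporary spasm and local erythema. The second is a 12-row table of potential adverse effects. Two of its rows read "Significant discomfort, pain, cramping, tenderness, soreness, muscle spasm following the procedure which results in medical intervention" and "Erythema lasting longer than 2 weeks". The last row, Other, takes in "Any other untoward medical event determined by the Investigator to be an adverse event, regardless of the relationship to the device or treatment".

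Section 2.12 closes with advice to subjects: "Subjects will be encouraged to call the study site if they experience any unusual effects (e.g., severe discomfort etc.)".

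**The concern.** Read alone, the Section 6.2 table looks like a set of case definitions. Muscle pain, spasm and erythema appear in both lists. In the adverse-effect table they appear only when severe, prolonged, treatment-stopping or needing medical intervention. A coordinator might conclude that ordinary soreness or brief redness is an expected effect and not an AE, and that the Other row leaves it to local judgement. The advice in Section 2.12, which stresses unusual effects, leans the same way. No visible sentence says which section governs.

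These are the events the protocol itself expects, so whether they are counted could largely set the headline safety figure. With up to 20 sites, practice could vary. An event that was never recorded cannot be recovered at analysis, and measured against Section 2.18 the error could only lower the frequency.

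**Working it through.** **1. The two sections side by side.**

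| Point | Section 2.18 | Section 6.2 |
|---|---|---|
| Place in the document | Adverse-event section of the study protocol | Risk/benefit analysis |
| Purpose | Defines, records and reports events | Describes what might happen |
| Severity or duration threshold | None | In all four rows on erythema or on discomfort, pain and spasm |
| Instruction to record | All AEs go on the CRF | None |
| Instruction not to record | None | None |

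The four thresholded rows are severe erythema, prolonged erythema (over 2 weeks), discomfort during the procedure (leading to discontinuation) and discomfort afterwards (leading to medical intervention). There is one recording rule and one risk description, so the sections do not give two conflicting rules.

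**2. Applying the rule.** Take mild soreness the day after a treatment. It is an untoward occurrence, so it is an AE under Section 2.18. If the Investigator judges it possibly related, it is also device-related. It goes on the CRF and counts in the endpoint. In Section 6.2 it fits the Other row, whose wording is close to the Section 2.18 definition and sets no threshold.

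**3. Another reason for a separate anticipated list.** Section 2.18 defines an unanticipated adverse device effect partly by whether the effect was already identified in the plan in nature, severity or incidence. A list of anticipated effects serves that test. It does not make those effects non-events, and Section 6.2 itself calls most of them side effects.

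**4. Opportunities to capture events.** Table 2 marks an AE assessment at all four treatment visits (two in Week 1, two in Week 2) and at both follow-up visits. Effects of treatments 1 to 3 therefore meet another scheduled assessment at the next treatment visit. Only effects arising after treatment 4 wait for the 4-week visit, which is 4 − 1 = 3 to 4 + 1 = 5 weeks later, unless reported spontaneously as Section 2.18 allows.

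**5. Size.** The plan states no AE rate, so there is no figure to reproduce. For scale, assume:

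- equal enrolment: 200/20 = 10 subjects per site;
- a proportion p of subjects whose only device-related events are mild anticipated ones;
- k sites that do not record them.

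Shortfall in the overall frequency = p × k/20.

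| k | p = 10% | p = 50% |
|---|---|---|
| 0 | 0 | 0 |
| 1 | 0.10 × 1/20 = 0.5 points (1 of 200) | 0.50 × 1/20 = 2.5 points (5 of 200) |
| 10 | 0.10 × 10/20 = 5 points (10 of 200) | 0.50 × 10/20 = 25 points (50 of 200) |

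Both p and k are assumptions. The model also uses an overall subject-level frequency, whereas Section 2.16.3 tabulates each type of event.

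**The case for a change.** The best case for a change is that sites are trained on the whole plan and not on Section 2.18 alone. Several rows of the Section 6.2 table are worded like diagnostic criteria, and the Other row reads more like a CRF category than a risk. If the two readings were really open, the choice would outweigh sampling error. At n = 200, an assumed 0 subjects with events gives an exact 95% interval of 0 to 1.8%, and an assumed 60 subjects (30%) gives 23.7% to 36.9%. One clarifying sentence would cost almost nothing.

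Part of this stands. Section 6.2 could be misread, no visible passage rules the misreading out, and mild effects after treatment 4 do depend on recall or a spontaneous call. But the contrast between those intervals assumes that every site adopts a reading that Section 2.18 does not support. The Section 2.12 advice concerns when a subject should telephone and sets no collection rule. Reliance on Investigator judgement is not peculiar to the Other row, because Section 2.18 relies on it for relatedness too.

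The visible text is also incomplete. Steps at the treatment visits, two assessment sections and a Table 2 row marked at every treatment and follow-up visit are redacted, and the CRF instructions are not in the documents. Silence in what remains is weak evidence of a gap.

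**Conclusion.** The concern does not call for a change. Section 2.18 makes mild device-related pain, spasm and erythema recordable, and Section 6.2 does not take that away. What remains is a possible misreading at site level, which ordinary conduct can deal with. The plan provides standardized CRFs (Section 3.1), training on data collection and form completion, and monitoring of CRFs against source records (both Section 3.4).

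The shortfall is zero if sites follow Section 2.18. Otherwise its direction is downward and its size cannot be estimated from the documents; the 0 to 25 point range in the table is arithmetic on assumed p and k. The endpoint is descriptive, in a non-randomized study with no visible safety hypothesis or decision limit, so no formal conclusion turns on it. Because Section 2.16.3 already reports events by type, recorded muscle pain and erythema will be visible without an extra table. An analyst would naturally use the As-Treated set of Section 2.16.2, which holds all treated subjects.

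The heading "Adverse Device Effect (AE)" in Section 2.18 reuses the abbreviation for adverse event. That is a clerical slip, and the definition beneath it is clear. A sentence saying that Section 2.18 governs recording would be harmless but optional.
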